Consented patients with *MC1R* genotypes not selected for randomization. We will randomly select only 500 white, non-Hispanic participants from each of the *MC1R* risk categories (low and high) to participate further in our study. Therefore, some participants may receive a letter from the research team thanking them for their interest in our research project and informing them that they were not selected for further study participation. The letter will inform patients about their *MC1R* risk status and provide educational materials highlighting standardized information for the general population about melanoma, melanoma risk, melanoma prevention (i.e. sun protection and skin examination), and sun protection behaviors for children.

Randomization. For our white, non-Hispanic population we will randomize 500 participants with high risk and 500 participants with low risk *MC1R* genotypes. 50% of high risk and low risk individuals will be randomly allocated to the intervention and placebo arm (250 participants per arm) using permuted blocks, with a block size of four, and equal weighting scheme.

For our H/L population we will randomize 200 participants with high risk and 200 participants with low risk *MC1R* genotypes, with 50% of high risk and average risk individuals will be randomly allocated to the intervention and placebo arm (100 participants per arm).

Because our prior work does not indicate an increased risk of melanoma associated with low risk *MC1R* genotypes, we focus our study hypothesis on the intervention effect among persons with high risk *MC1R*. However, analysis of the efficacy of the intervention among participants in the low risk *MC1R* genotype group will enable us to assess any potential negative impact upon prevention behaviors that feedback of a 'negative' genetic test results may produce. Moreover, because the health educator will be blinded to the *MC1R* genotype status of participants randomized to the placebo arm, the addition of the low risk group affords implicit control of potential bias introduced by the health educator's knowledge of participant *MC1R* status at the time of the education session.

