Participants reporting sun-sensitive phenotypes.

Participants having had a skin examination within the past year.

Exclusion Criteria for our H/L population:

Children under the age of 18

Participant whose medical records or self-report indicate an ethnicity aside from Hispanic.

Participants having had a skin examination within the past year.

Participants with a personal history of melanoma and/or more personal history of more than one SCC and/or BCC.

Primary Outcome of the Study:

Primary outcomes will be measured using an adapted version of a published survey assessing measures of sun exposure and sun protection (Glanz et al. 2008) (see **Appendix**).

For Aims 1 and 2, the 14-item measure for adults (Section A) will be used. Section A is completed by the study participant and elicits responses about his/her own sun protection and skin examination behaviors including: average number of hours spent outside during weekdays and weekend days in the summer; number of red or painful sunburns during the past 12 months; frequency of sun protection behaviors when outside in the summer sun; frequency of intentional tanning; color of untanned skin; and skin examinations by a health professional or by the study participant him/herself or his/her partner.

For Aim 1, the primary outcome of interest is average number of hours spent in the sun per week between 10am – 4pm. This measure will be a weighted average of the first two questions on the survey asking about number of hours spent outside during the hours of 10 to 4 on weekdays (Section A, Q1) and on weekend days (Section A, Q2). We will tailor the timeframe of Q1 and Q2 given in Glanz et al. to fit our Aim and our timeline (Glanz et al. 2008). At baseline the timeframe will be “in the past 12 months”; and for our white, non-Hispanic population at the 6 and 12 month follow-up surveys and

at 3 and 9 month for our H/L population, the timeframe will be “in the past 6 months” for our white, non-Hispanic populations and “in the past 3 months” for our H/L population.

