For Exploratory Aim 3, the 12-item measure for children age 10 years or younger as reported by the study participant (Section B) will be used. Study participants with at least one child 10 years of age or younger will complete Section B, and those participants with more than one child within this age range are instructed to answer questions in this section thinking about the oldest child. Section B elicits responses about sun protection behaviors of the child, including number of red or painful sunburns over the past year for white, non-Hispanics and over the past 9 months for our H/L populations.

Since intermittent sunburns in adolescence are strongly associated with future melanoma risk (Armstrong et al. 1993, Gandini et al. 2005), the outcome of particular interest for our exploratory aim is the number of red or painful sunburns that lasted a day or more over the past timeframe. This outcome is measured by Section B, Q5, with a range of possible responses of 0 through 5 times (5 indicating 5 or more red or painful burns). We will tailor the timeframe to correspond to the baseline, 6 or 12 month survey for white, non-Hispanic participants and at baseline, 3 or 9 months survey for H/L participants).

STATISTICS

There will be no merging of data between the white non-Hispanic study population and

the H/L study population data. We will conduct mutually exclusive analyses within each of these two study populations.

Non-Hispanic study population

For our white, non-Hispanic population, the number of participants, 500 with high risk *MC1R* genotypes required to participate in this study was based upon the power calculations below.

Study power, Aim 1. We determined that randomizing 500 participants with high risk *MC1R* variants (250 each to the intervention and placebo arm) ensures 80% power to detect mean differences in hours of sun exposure of 0.17, 0.50 and 0.84, respectively, when the estimated standard deviation of the observed means is equal to 1, 3 and 5, respectively, when comparing participants with high risk genotypes who are randomized to intervention to participants with high risk genotypes who are randomized to placebo. These calculations are based on two-sided, alpha=0.05 level tests assuming a conservative auto-correlation equal to 0.1 to account for the repeated measures of participants over time, and a conservative 20% study attrition.

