Aim 1. We will use a linear GEE regression model with main effects for the intervention (standard risk and prevention plus genetic education versus standard risk and prevention education only), time, and the interaction terms between the intervention and time. The interaction term will be the main test of interest as it assesses average departure from the slope due to the intervention. We will include other covariates related to dropout or involving potential baseline imbalances between the intervention groups as appropriate, as well as month of completion of the questionnaires to account for seasonality.

We will perform analyses to test whether participants and eligible non-participants differ on basic demographic variables using cross-sectional logistic or linear regression models for binary or continuous factors, respectively. We will perform attrition analyses to determine whether participants and dropouts differ on key variables. We will include these factors in the above ITT model to see if they affect the results. A few randomly missing observations have only a slight impact on power and do not introduce bias. However, large numbers of non-randomly missing values can bias results.

We also will conduct mediator analyses to determine whether the effect of the intervention on prevention behaviors is explained by health beliefs or cancer distress. We will use a series of models to examine whether (a) the intervention is predictive of the mediator, (b) the mediator is predictive of prevention behaviors in a multivariable model controlling for the intervention, and (c) the addition of the mediator to a

multipredictor model for prevention behaviors attenuates the estimated coefficient for the intervention. To assess mediation effects, we will use the approaches by Imai et al., which are available through add-on packages to existing statistical software (such as R and STATA) (Imai et al. 2010, Imai et al. 2012). Similar to the method of Preacher and Hayes (Preacher et al. 2008), their methods employ bootstrapping to estimate mediating causal effects . These analyses will be used to estimate the direct effect of the intervention via pathways other than through the posited mediator, its indirect effect via the mediator, and the degree of mediation. This approach will allow us to quantify the effect of the intervention due to the potential mediator (if any), which can inform future interventions or prevention strategies.

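### Aim 1 rests on arm × time, apparently with baseline hours as an outcome; this is valid but inefficient, by an amount that depends on the correlation and the effect shape, and the time coding is not stated.

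*Combined protocol and SAP*

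**What the plan says.** STATISTICS, Aim 1, specifies a linear GEE with intervention, time and their interaction, and adds: "The interaction term will be the main test of interest as it assesses average departure from the slope due to the intervention". It lists no time points. It speaks of interaction terms in the plural and then of a single term and a slope, so the coding of time is open. Covariates are limited to those tied to dropout or baseline imbalance, used as appropriate, plus month of completion. Baseline hours are not named.

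STATISTICS, Aim 2, says its model follows the Aim 1 outline and gives the times as 0, 6 and 12 months.

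Study power, Aim 1 (white, non-Hispanic cohort) has "250 each to the intervention and placebo arm" among high-risk participants. It claims that this "ensures 80% power to detect mean differences in hours of sun exposure of 0.17, 0.50 and 0.84" "when the estimated standard deviation of the observed means is equal to 1, 3 and 5, respectively", "assuming a conservative auto-correlation equal to 0.1 to account for the repeated measures of participants over time" and allowing for 20% attrition.

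Under Primary Outcome of the Study, the recall period is the past 12 months at baseline and the past 6 months at each white, non-Hispanic follow-up. The study objectives ask about efficacy at both the short-term and the long-term follow-up.

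**The concern.** Under Randomization, "50% of high risk and low risk individuals will be randomly allocated to the intervention and placebo arm", so the arms have the same expected baseline hours. An interaction that includes the baseline row subtracts each arm's observed baseline from its follow-up. That subtraction removes no bias, and when visits are weakly correlated it adds variance. The unequal recall periods apply to both arms, so they do not bias the comparison, but they make a slope from baseline harder to interpret.

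At stake is the precision of one of the two primary outcomes. A reduction in sun hours present at both follow-ups could be missed by the planned test although the same data would show it. If time is a single linear term, the model also gives no separate 6-month and 12-month effects.

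**Working it through.** **Inputs.** From the plan: 250 per arm, 20% attrition (taken here as 200 analysed per arm), correlation r = 0.1, two-sided 0.05, 80% power. Assumed: equal SD at each visit and exchangeable correlation. Effects are in SD units. Detectable difference = 2.80 × √(2v/n) and power ≈ Φ(d/√(2v/n) − 1.96), where v is the per-person variance of the contrast.

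**The plan's own figure.** Two readings give 0.17, 0.50 and 0.84 after rounding.
- Slope per 6-month interval over 0, 6 and 12 months: v = (1 − r)/2 = 0.45. With n = 250 and no attrition, 2.80 × √(0.90/250) = 0.168, and ×3 and ×5 give 0.504 and 0.840. This would mean about 0.34 SD at 12 months.
- Mean of three visits: v = (1 + 2r)/3 = 0.40. With an average n of 225 (losses of 0, 10 and 20% across visits, an assumption), the results are 0.167, 0.501 and 0.835.

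With n = 200 neither fits: 0.188 for the slope and 0.177 for the mean of three. The plan does not say which contrast was powered.

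**Variance of each contrast.**
- Linear slope, expressed at 12 months: 2(1 − r)
- Mean follow-up minus baseline: (1 + r)/2 + 1 − 2r
- Baseline-adjusted mean of both follow-ups: (1 + r)/2 − r²

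| r | Slope | Mean change | Adjusted mean | Loss, mean change | Loss, slope (sustained effect) |
|---|---|---|---|---|---|
| 0.1 | 1.80 | 1.35 | 0.54 | 60% | 70% |
| 0.3 | 1.40 | 1.05 | 0.56 | 47% | 60% |
| 0.5 | 1.00 | 0.75 | 0.50 | 33% | 50% |
| 0.7 | 0.60 | 0.45 | 0.36 | 20% | 40% |

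Loss is 1 minus the ratio of the adjusted variance to the planned one. Mean change and adjusted mean estimate the same quantity, so that column does not depend on effect shape. The slope column assumes the same effect at 6 and 12 months.

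**A 12-month-only contrast at r = 0.1.** Change from baseline has variance 1.80 and the adjusted value has 1 − r² = 0.99. The loss is 1 − 0.99/1.80 = 45%.

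**Detectable difference at r = 0.1, n = 200.** Slope 0.376 SD, mean change 0.326 SD, adjusted mean 0.206 SD.

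**Power at r = 0.1 for a sustained 0.25 SD effect.**
- Slope: 0.25/√(3.60/200) = 1.863, giving 46%.
- Mean change: 0.25/√(2.70/200) = 2.152, giving 58%.
- Adjusted mean: 0.25/√(1.08/200) = 3.402, giving 92%.
- Categorical time, 2-df interaction: the two changes have variance 1.80 and covariance 0.90, so the noncentrality is 0.25² × 100 × 2/2.70 = 4.63, giving 47%.

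**Time limited to 6 and 12 months.** The interaction is then the 12-month difference minus the 6-month difference. For a sustained effect this is d − d = 0, so power equals alpha.

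**At the plan's 0.168 SD.** Adjusted mean: 0.168/√(1.08/200) = 2.286, giving about 63%. Mean change gives 30% and slope 24%.

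**Simulation (400 runs, 200 per arm, r = 0.1, sustained 0.3 SD).** Slope test 59.5%, adjusted GEE 97.8%. Adding baseline hours as a covariate while keeping the baseline row left the slope test at 59.5%, so the plan's imbalance-covariate clause does not recover the loss.

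**The case against.** Several points on the other side stand.

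- **The model is partly inferred.** The baseline row comes from the Aim 2 time points and the slope wording, and the plural interaction terms would fit visit-specific contrasts. A reader might infer that the plan commits Aim 1 to one linear slope from baseline. The text does not settle this. The other readings do no better, however, as the 47% and the zero contrast show.
- **The size is not fixed.** A reader might infer that the plan always discards more than half the information. That does not follow. The plan calls 0.1 conservative, and a low correlation makes a change or slope test look worst. The loss shrinks as the correlation rises, and it is 45% at 0.1 for a 12-month-only contrast.
- **The covariate is not the main source of gain at 0.1.** The unadjusted follow-up mean already has variance (1 + 0.1)/2 = 0.55, against 0.54 adjusted. Nearly all the gain comes from not subtracting baseline. The covariate matters at higher correlation: at 0.5 it takes 0.75 to 0.50.
- **Equal SDs are unverified.** The recall periods differ. If baseline SD were 0.7 of follow-up SD (illustrative), mean-change variance at 0.1 would be 0.55 + 0.49 − 0.14 = 0.90 and the loss 40%.
- **The averaged test is not best for every effect.** If an effect d appeared only at 12 months, the averaged arm test would carry (d/2)²/0.54 = 0.46d², less than the slope's d²/1.80 = 0.56d². The objectives ask about both follow-ups, which favours the average, but arm × visit should be kept.

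**Conclusion.** The point holds as one of efficiency and specification. Under randomisation the planned test is valid: nothing here shows bias or an inflated type I error, and a reader should not infer either.

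With 200 analysed per arm, equal SDs and exchangeable correlation, the like-for-like loss runs from 60% at a correlation of 0.1 to 20% at 0.7. For a sustained effect the slope test loses 70% to 40% over the same range. The true correlation, the per-visit SDs and the effect shape are not documented.

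A reader might also infer that changing the analysis makes the printed power correct. It does not: at 0.168 SD and a correlation of 0.1 the adjusted analysis has about 63%, so the power text needs its own correction. For the Hispanic/Latino cohort no correlation is stated and the visits are at 3 and 9 months, so the gain there is not quantified.

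**What to change.** In STATISTICS, Aim 1:

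1. State the time points and whether time is linear or categorical.
2. Model only the follow-up hours (6 and 12 months; 3 and 9 months in the Hispanic/Latino cohort) by GEE with arm, visit, baseline hours and month of completion.
3. Make the arm effect averaged over both visits the main test.
4. Keep arm × visit to give the separate short-term and long-term contrasts.

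A close alternative keeps baseline as an outcome but gives both arms a common baseline mean. In GEE this depends on the working correlation, which must then be specified.

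The cost is SAP wording, since baseline hours are already collected. Two small rules are needed: how a missing baseline value is handled, and how randomised participants with no follow-up are treated. The General approach promises intention-to-treat analysis whatever number of follow-ups is completed, and a follow-up-only model drops those with none. The detectable difference should be restated for the chosen contrast, at about 0.21 SD with 200 per arm and a correlation of 0.1.

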MC1R variants in Hispanic populations living in the Tampa Bay area. Melanoma incidence is trending upward among Hispanics living in the United States and Puerto Rico (Gonzalez-Fernandez and Sanchez, 1999; Hu et al. 2009). Of particular concern is the poorer overall survival from melanoma among Hispanics due to diagnoses at late stage disease (Hu et al. 2009; Rouhani et al. 2010; Jaimes et al. 2013). However, information on the prevalence and distribution of *MC1R* variants in Hispanic individuals is limited. Knowledge of the spectrum and distribution of the *MC1R* genotypes among Hispanic individuals will lay the foundation for future investigations of whether *MC1R* variants are robust markers of melanoma risk in this population, and by extension whether interventions based on inheritance of high-risk *MC1R* genotype—with the goal of increasing melanoma prevention behaviors—may be generalizable to Hispanic populations.

Using *MC1R* genotype to impact skin cancer risk behaviors in Hispanics/Latinos. The incidence of melanoma and/or keratinocyte (i.e., squamous cell and basal cell) skin cancers is trending upward among Hispanic/Latinos (H/L) living in Florida and Puerto

Rico (Gonzalez-Fernandez and Sanchez, 1999; De La Torre-Lugo et al. 2010; Hu et al. 2009). Feedback of genetic risk information has been suggested to motivate skin cancer prevention behaviors, and H/L are receptive to receiving this type information (Smit et al. 2016; Lynce et al. 2016). These activities may be important to H/L populations who have decreased awareness and risk perception of melanoma.

STUDY PURPOSE AND HYPOTHESIS

The primary objectives of this project are to:

- **Evaluate the impact of receipt of *MC1R* genotype on personal sun protection behaviors.** Determine the efficacy of a risk and prevention education session, which includes feedback of inherited *MC1R* genotype and corresponding information about genetic risk, to decrease sun exposure and increase sun protection behaviors at both short term (6 months) and long term (12 months) follow-up for our white, non-Hispanic population; for our H/L population, follow-up will occur at 3 and 9 months.

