- **Evaluate the impact of receipt of *MC1R* genotypes on skin awareness and examination.** Determine the efficacy of a risk and prevention education session, which includes feedback of inherited *MC1R* genotype and corresponding information about genetic risk, to increase skin examinations at both short term (6 months) and long term (12 months) follow-up for our white, non-Hispanic population; for our H/L population, follow-up will occur at 3 and 9 months.

The secondary objective of this project is to:

- **Evaluate the impact of receipt of *MC1R* genotype on sun protection behaviors in children of study participants.** Determine whether a risk and prevention education session, which includes feedback of inherited *MC1R* genotype and corresponding information about genetic risk, can decrease the number of sunburns at both short term (6 months) and long term (12 months) follow-up in the children of white, non-Hispanic study participants; for our H/L study participants, follow-up will occur at 3 and 9 months.
- **Explore the prevalence of *MC1R* genetic variants in Hispanics living in the Tampa Bay.** We hypothesize that non-synonymous variants at *MC1R* known to be high-risk in non-Hispanic white populations of European ancestry will be readily identified among Hispanics living in the Tampa Bay area, but will occur as lower prevalence.
- **Correlate the degree of European genetic ancestry with *MC1R* variation in this Hispanic population.** We will genotype germline DNA using Ancestry Informative Markers to determine percent European (African and Asian) ancestry and correlate genomic ancestry with genetic variation in *MC1R*. We hypothesize that the prevalence of non-synonymous variants at *MC1R* observed among Hispanics living in the Tampa Bay area will decrease as the proportion of non-European (i.e. African or Asian) genomic ancestry increases.

PROJECT DESCRIPTION

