For our H/L population patients eligible for study participation will identify themselves as H/L, 18 years of age and older, able to read and speak either Spanish or English fluently; there will be no exclusions based on reported race. Individuals will be excluded from the study if they have had or completed a full skin examination over the past year, report a prior history of melanoma, report having more than one SCC, or report having more than one BCC.

After signing informed consent, a biologic sample (saliva) will be collected for the purpose of DNA extraction determination of *MC1R* genotypes. All participants who carry high risk *MC1R* genotypes and a proportion of those who carry low risk or no *MC1R* variants will be randomized to the control or intervention arm.

For our white, non-Hispanic population information on demographics and cutaneous pigmentation will be collected using a structured screening instrument. For our H/L population demographics and cutaneous pigmentation information will be collected at baseline. Information on personal sun protection behavior and skin examinations will be obtained via structured questionnaire instruments at baseline and at two follow-up times, 6 and 12 months for white, non-Hispanic population, 3 and 9 months for our H/L population. Information on potential mediators of effect will be collected at the two follow-up times using structured questionnaire instruments. The H/L intervention portion of the study is funded as a main project on Moffitt's U54 competitive renewal award for which the project timeline totals 3 years (instead of 5 years for our white, non-Hispanic population study funded under ACS). Because of the difference in the duration of the

study it was necessary to be flexible with the timing of our outcome measures; we selected 3 and 9 months follow-up for our H/L population instead of 6 and 12 months to assure two-post intervention measurement with the project timeline. Additional constructs capturing fatalism, familism and acculturation will be obtained for H/L population at baseline.

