Study power, Aim 2. We estimate a 20% incidence of having a skin examination with the past 9 months among control participants, with a range of 15% to 35%, and estimate study attrition of 20%. Using these estimates, we determined that randomizing 400 participants with high-risk *MC1R* variants (200 per study arm) ensures 80% power to detect an odds ratio of at least 1.95 to 1.73 when comparing participants with high-risk genotypes randomized to intervention versus those randomized to control for the skin examination (yes/no) outcome.

General approach. All analyses will be done within SAS, version 9 or later, primarily using PROC UNIVARIATE, FREQ and GENMOD. In the primary analyses, we will use an intention-to-treat (ITT) approach in which participants are analyzed in their randomized conditions regardless of the number of interventions or number of follow-up assessments they complete. Two-sided tests will be used for all hypotheses. We will assess the data for missing and out-of-range values with basic statistical procedures, including univariate statistics and graphs (histograms, box and whisker plots, scatter plots, and Q-Q plots). We will investigate data quality and integrity before any statistical modeling to ensure unbiased estimation.

The primary aim of this proposal is to test for significant ITT differences in the proportion of study subjects participating in skin prevention behaviors over the 12-month follow-up period by comparing those who receive a risk and prevention education intervention that includes feedback of *MC1R* genotype to those who receive a risk and prevention education session that includes only standard information. Our two primary outcomes of interests are (1) the average hours per week (weekdays and weekend) spent outside between 10am – 4pm; and (2) the completion of a full body skin examination for skin cancer (yes/no) by self, partner or clinician.

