Aim 2. Hypothesis testing for the binary outcome of full-body examination (yes/no) will follow the general analytic outline used in Specific Aim 1. This outcome will be modeled using the logistic framework of the GEE approach (i.e. specifying a logit link function), which properly accounts for the induced correlation from the repeated measures on participants over time, to assess ITT differences. These ITT differences comparing the probability of skin examinations will be presented as odds ratios with corresponding 95% confidence intervals where models will include main effects for intervention (standard risk and prevention plus genetic education versus standard risk and prevention education only), time (0, 6, and 12 months), and interaction term between the intervention and time. The interaction term will be used to test for possible differences in effects over time in the two study arms as the main test of interest. In addition, the logistic GEE model will contain baseline covariates and variables related to study participation and/or attrition as appropriate.

Exploratory Aim 3. We will use the GEE Poisson or ordinal regression models as appropriate with main effects for the intervention, time, and interaction term between the intervention and time, and will adjust for date of study enrollment to account for seasonality. Specifically, we are interested in estimating the intervention's efficacy in reducing the average number of red or painful sunburns in children.

All statistical analyses will be conducted by a member of the Biostatistics Core under the direction supervision of [name].

Analyses among individuals with low-risk *MC1R* genotypes will be conducted in a similar fashion to those detailed above. Because we do not expect to see ITT differences in prevention behaviors comparing those who receive a risk and prevention education intervention that includes feedback of *MC1R* genotype to those who receive a risk and prevention education session that includes only standard information among the low-risk group, power analyses are omitted.

Pilot study Aim 1. The overall prevalence of *MC1R* genotypes will be calculated with corresponding 95% confidence intervals.

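### The primary objectives claim efficacy at both follow-up surveys, but the single main test is an arm-by-time slope that, with linear time, does not test the short-term one, and no deciding survey is named

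*Combined protocol and SAP*

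**What the plan says.** - **Objectives (STUDY PURPOSE AND HYPOTHESIS).** The first primary objective is efficacy "to decrease sun exposure and increase sun protection behaviors at both short term (6 months) and long term (12 months) follow-up". The second is efficacy "to increase skin examinations at both short term (6 months) and long term (12 months) follow-up". Those times are for the white, non-Hispanic population; "for our H/L population, follow-up will occur at 3 and 9 months".
- **Survey schedule (RESEARCH PROCEDURES, Summary).** Behaviour is measured at baseline and at two follow-ups: "6 and 12 months for white, non-Hispanic population, 3 and 9 months for our H/L population".
- **Primary aim (STATISTICS, General approach).** The aim is restated as a difference "in the proportion of study subjects participating in skin prevention behaviors over the 12-month follow-up period". No survey is singled out. The sentence speaks only of proportions, although one of the two outcomes is mean hours outdoors, and it gives no 9-month period for H/L.
- **Main test, Aim 1 (STATISTICS, Aim 1).** The linear GEE model has main effects for intervention, "time, and the interaction terms between the intervention and time". Then: "The interaction term will be the main test of interest as it assesses average departure from the slope due to the intervention".
- **Main test, Aim 2 (STATISTICS, Aim 2).** The logistic GEE model uses the same terms with time at 0, 6 and 12 months, and the interaction is to test for "possible differences in effects over time in the two study arms as the main test of interest". No H/L times are given here.

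Nowhere does the plan state whether time is continuous or categorical. It gives no contrast at 6 months (or 3 months), no order between the two surveys and no division of alpha between them.

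**The concern.** An objective that claims an effect at each of two surveys needs a test that can respond to each of them. A linear slope over three waves compresses the trajectory into one number, and with these survey times that number is driven by the last survey against baseline. An effect present at the first survey and gone by the second would be reported as no effect. In H/L it would push the estimate in the wrong direction, even though short-term efficacy is half of each primary objective. If time is categorical instead, there are two interaction coefficients per outcome and no statement of what counts as success. In both cases the criterion for a positive result on both primary outcomes is left open.

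**Working it through.** **Inputs.** From the documents: survey times 0/6/12 and 0/3/9 months; 250 (white, non-Hispanic) and 200 (H/L) high-risk participants randomized per arm; 20% attrition; two-sided alpha 0.05. Correlation 0.1 is stated for the white, non-Hispanic Aim 1 calculation and is also used here for H/L. Assumed: an effect of 0.35 SD in the favourable direction, equal variances, exchangeable correlation, and completers only, so 0.8 × 250 = 200 and 0.8 × 200 = 160 per arm.

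**1. The plan's own figure.** Study power, Aim 1 gives detectable differences of 0.17, 0.50 and 0.84 for SD 1, 3 and 5. For a linear slope per 6-month step, the difference is (1.960 + 0.842) × SD × √(2f/n), with f = (1 − 0.1)/2 = 0.45. With n = 250, √(0.90/250) = 0.060, giving 0.168, 0.504 and 0.840, which matches. With n = 200 it gives 0.188, 0.564 and 0.940. The match supports the slope reading but does not prove it. The mean of three waves, f = (1 + 0.2)/3 = 0.40, with n = 225 gives 0.167, 0.501 and 0.835, which round to the same values.

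**2. Slope weights, proportional to t minus mean(t).**
- 0/6/12: mean 6, deviations (−6, 0, +6), so weights (−1, 0, +1).
- 0/3/9: mean 4, weights (−4, −1, +5).

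The 6-month zero also holds under AR(1), and the 3-month weight stays negative under AR(1) for correlations 0.1 to 0.9. With monotone attrition to 20%, the first-survey weights, scaled to the full span, become about +0.07 (from 0) and −0.15 (from −9/42 = −0.214).

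**3. Standard errors in SD units.** For weights w, variance = (2/n) × (1 − 0.1) × Σw², since the weights sum to zero.
- White, non-Hispanic slope: √((2/200) × 0.9 × 2) = 0.134.
- H/L slope: √((2/160) × 0.9 × 42) = 0.687.
- First-survey change from baseline, weights (−1, +1, 0): 0.134 and √((2/160) × 0.9 × 2) = 0.150.

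**4. Effect at the first survey only, pattern (0, 0.35, 0).**
- White, non-Hispanic slope: z = 0, so power is 5%, the alpha level.
- H/L slope: z = −0.35/0.687 = −0.51. Significant results are 7.3% in the wrong direction and 0.7% in the right one.
- Change from baseline: z = 0.35/0.134 = 2.61 and 0.35/0.150 = 2.33, so power is 74% and 65%.
- Joint 2-df interaction: noncentrality 0.35² × (2/3) × n/1.8 = 9.07 and 7.26, so power is 77% and 67%.

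**5. Other patterns, slope test.**
- Sustained (0, 0.35, 0.35): z = 0.35/0.134 = 2.61 and 0.35 × (5 − 1)/0.687 = 2.04, so power is 74% and 53%.
- Half remaining (0, 0.35, 0.175): z = 0.175/0.134 = 1.30 and (5 × 0.175 − 0.35)/0.687 = 0.76, so power is 26% and 12%.

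**6. Aim 2, linear time on the logit scale.** Take a 20% control rate at both follow-ups and an intervention rate of 31% at the first survey only (odds ratio (0.31/0.69)/(0.20/0.80) = 1.8). With a 20% baseline rate, the interaction over the span is 0.00 log odds (0/6/12) and −0.13 (0/3/9). Entry excludes people examined in the past year, so baseline should be much lower. At an assumed 2% the values are −0.32 and −0.38.

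**The case against.** **Time may not be linear.** The plan never says that it is. Aim 1 also uses the plural for the interaction terms, and Aim 2 lists three times and does not mention a slope. With categorical time the first survey enters the test, and a joint 2-df test would hold 5% and detect the transient pattern with 77% and 67% power. This stands, so the weights are conditional. A reader might infer that the short-term objective is certainly untested; the documents support that only under linear time. The exact zero also needs complete, balanced data, and the H/L weights rest on times taken from the survey schedule.

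**Error inflation.** A reader might infer that categorical time inflates the false-positive rate: two tests at 0.05, with either sufficing, give 9.1% when the two changes from baseline correlate 0.5. No section states an either-survey rule. The objectives say both, and requiring success at both would not inflate error, nor would a joint test. Inflation is therefore not a consequence of the plan as written.

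**An early, fading effect is only an illustration.** A reader might take it as the expected pattern. The documents do not forecast it. The background cites a skin-examination intervention trial with a 19.3% difference after 12 months, and here a summary letter reinforces the packet and call. For a sustained effect in the white, non-Hispanic population, the slope has the same 74% power as the 6-month change.

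**Comparator.** A cross-sectional comparison at the first survey would show 94% and 88% power, but it ignores baseline. The interaction model measures change from baseline, so 74% and 65% are the like-for-like figures.

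**The 12-month wording** in the General approach can be read as an observation window, not a rival contrast. That is fair. It still names no deciding survey.

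**Conclusion.** The concern holds in conditional form. Two points need no assumption about time: the objectives claim efficacy at both surveys, and the plan names neither a deciding survey nor a rule linking the surveys to the main test. Under linear time, which is the natural reading of the Aim 1 sentence, the first survey has zero weight (white, non-Hispanic) or negative weight (H/L), and the short-term objective is not tested. In the assumed first-survey-only case the cost is 5% power against 74% for the white, non-Hispanic population, and an expected z of −0.51 against 65% power for H/L. These figures rest on a 0.35 SD effect, correlation 0.1, and 200 or 160 completers per arm. The loss concerns short-term and waning effects; a sustained effect still moves the slope. Under categorical time the weights fall away, but the deciding coefficient or joint test remains unspecified.

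**What to change.** - **Model (STATISTICS, Aims 1 and 2).** Fit time as categorical: 0/6/12 months, and 0/3/9 months for H/L.
- **Contrasts.** Replace the slope test with named between-arm contrasts at each follow-up survey, for each outcome. State whether each is a change from baseline or a baseline-adjusted difference.
- **Decision rule.** State one rule that controls alpha within each outcome: for example a fixed sequence in a stated order, or a 2-df joint test followed by the two contrasts. The order should follow from the objectives. If the final survey comes first, a purely transient effect would reach the short-term test only about 5% of the time.
- **Slope.** Report it as descriptive.
- **General approach.** Align the aim sentence with these contrasts: mean hours for the first outcome, odds ratio for the second, and 9 months for H/L.
- **Study power, Aim 1.** Check that the detectable differences refer to the chosen contrast. If the slope formula was used, 0.50 hours at SD 3 is a difference per 6-month step, about 1.0 hour at 12 months.

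**Cost.** No new data or participants are needed, because both surveys are already planned. In a fixed sequence, the survey tested second is supportive only if the first fails, and the power statement may have to be restated. For white, non-Hispanic participants with complete data, the slope contrast already equals the 12-month change from baseline, so using that contrast loses nothing.
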